Franke AA et al., in 2016 conducted a pilot study to further explore the pharmacokinetics of AN's alkaloid as those assessment of biomarkers was very in need to evaluate the effectiveness of BQ cessation program that was targeted to reduce the oral cancer burden in the high-risk areas in Hawaii. The study found that AN alkaloids; **arecoline, guvacoline, guvacine, and arecaidine were detected in saliva of all participants and peaked within the first 2 hours post-chewing before returning to baseline levels after 8 hours**. The salivary chavibetol was reported in participants consuming betel leaves in their quid and it peaked 1-hour post-chewing. Thus, the study concluded the AN biomarkers from saliva can be followed up only on a short-term basis (≤ 8 h post-chewing). The study too claimed to find similar AN alkaloids from urine samples of the participants.

Franke AA et al. (2022) reported that **saliva bio verification results are valid to be used to verify the self-reported chewing status of participants ('quitter' or 'chewer') at day 22 follow-up to evaluate cessation program's effectiveness**. In the BENIT trial, among the quitters, the decrease in AN compounds were most significant for arecoline ($p=0.044$), followed by arecaidine ($p=0.042$) and nicotine ($p=0.011$). Among the current chewers, the significant decrease was noted only for hydroxycotinine ($p=0.004$).

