3.0 MATERIALS AND METHOD

3.1 Overview of the Study design

This is a comparative prospective community trial which utilises a cluster randomised controlled trial design involving a Bajau indigenous community in Sabah, Malaysia with a 1:1 allocation ratio. The clusters are Bajau villages that practises BQ chewing habits in Kota Belud district in Sabah. The Bajau villages are the unit of randomisation. There are 39 Bajau villages in Kota Belud, Sabah (Tahir Z et al., 2003).

The clustered randomised controlled trial study design was selected as there was a high tendency of crossover if both intervention and control groups are randomised within the same village. Individuals allocated to a control group may inadvertently receive some aspects of the intervention if they are in proximity to the individuals in intervention group (Hahn S et al (2005). Thus, clustered randomised trial is the best available design for researchers who evaluating intervention that operates at group level, that manipulates the social and physical environment and cannot be delivered to individual participants without any substantial risk of contamination (NIH, 2022).

The eligible villages will be randomised into intervention and control groups based on the required sample size. The intervention group will receive an educational booklet and a structured BQ cessation program which will be cross- culturally adapted first based on a clinical trial (BENIT) by Paulino YC et al. (2020) for a Malaysian high risk population. The control group will only receive an educational booklet.

Baseline information on participant's demographics, BQ chewing behaviours, BQ composition, BQ dependency levels, reasons for chewing, the readiness and self perceived barriers to cease habit will be obtained prior to the commencement of the intervention. The

same participants will be followed-up at 22-day and 3-month after commencement of intervention to assess their of quitting experience and impact of the intervention. Day 22 follow-up was kept in this study as it will enable study results to be compared with similar BQ cessation studies in other parts of the world such as in Pacific Islands (Moss J. et al., 2015 and Paulino YC et al., 2020).

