3.10.3.2 Implementation of the Study

Control Group

The community screening program for the control group will be organised at the community hall. Villagers who attended the screening program will first be registered and screened for eligibility to participate in the study (**Checkpoint 1**). The eligible participants will be briefed on the nature of the intervention and will be invited to participate. A copy of 'Patient Information Sheet' (PIS) (Appendix A) will be explained and given for reference about the study details and written informed consents (Appendix B) will be obtained from the villagers prior admitting them into the study.

Only consented participants will be interviewed by the trained interviewers (**Checkpoint 2**). Information regarding demographics details and baseline information of BQ chewing behaviours, BQ composition, BQ dependency levels, reasons for chewing, readiness and self-perceived barriers to quit will be obtained. No intra-oral clinical examination will be carried out in this study.

Upon completing of the interview, participants will be given an educational booklet which contains general information regarding AN and BQ, risk associated with BQ chewing behaviour, cessation strategies that are modeled after tobacco cessation and researcher's contact information. After an one-to one explanation about the educational booklet to the participants by the interviewer, they will be ushered to saliva collection counter (**Checkpoint 3**) to provide their baseline saliva sample. Participants will be thanked and given a token of appreciation before they are ushered out of the community hall.

Participants will be provided with an appointment card to return on the 22-day, 1-month and 3-month for follow-up. Follow-up questionnaire and saliva samples will be taken on 22-day and 3-month, whereas a community perception analysis will be performed at 1-

month together with completion of follow-up questionnaire. The summary of participant's flow for the control group is illustrated in Figure 3.6.

[figure not shown]

Figure 3.6 Summary of Participant's Flow for the Control Group in this study

Intervention group

Screening (Day 0)

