The subjects will be assigned into a group of seven participants and the appointments for each group participants will be given across the week. A total of 2 group sessions will be made in a day; a morning session and an afternoon session. Participants will be sought of their preferred time to increase participation in the intervention group.

[figure not shown]

Figure 3.7 Flow of Participants on the Screening of the study (Day 0)

1st Session (Day 1)

On the **1st session of the intervention (Day 1)**, attendance of all eligible and consented participants will be taken at **Checkpoint 1** and the nature of intervention will be introduced through a **brief talk**. The information that the participants will undergo 5 sessions of support and information group designed to assist them to quit BQ chewing habit over 22 days period will be emphasized and they will be reminded that their continuous commitment to the intervention is utmost important to their future cessation.

They will also be briefed that each support session will consume approximately 1-2 hours. It will be conducted by the main researcher in Malay language (Bahasa Melayu) and

translated by trained facilitators into Bajau language verbally. A translation script will be prepared before initiation of the intervention for standardization to minimise bias or any poor explanation in Bajau language.

After the brief introduction, an **educational talk** will be delivered to the study participants by the main researcher. The content of the talk will be based on the topics of the educational booklets (general information regarding AN and BQ, risk associated with BQ chewing behaviour through projection of captivating graphical aids, cessation strategies that are modeled after tobacco cessation and researcher's contact information) but in a more detailed and interactive manner. An aid of Microsoft Powerpoint multimedia presentation will be used. A two-way communication mode will try to be sought throughout the entire talk. Participants will be encouraged to participate actively during the educational talk session. The aim of the educational talk is to increase the chewer's awareness, motivation and to enhance their commitment to cease behaviour. Participants too will be encouraged to share their experience and their feelings of chewing BQ and what are the challenges they face while practicing this habit.

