Later, a discussion on the overall quitting experience will ensue. Participants who have relapsed and started chewing but are willing to attempt to quit again will be encouraged. **Strategies for managing thoughts** that could lead to relapse will be introduced. The participant's lifestyle changes that supports quitting will be reviewed. Usage of "excuses" for not chewing and employing "fake chew" will be reinforced.

The **Positive and Negative Thoughts Worksheet (Appendix L)** will be a strategy to manage the thoughts that participants might have through their quitting journey. This method is based on the notion that mood is related to the balance of the positive and negative thoughts. When negative thoughts outweighed the positive thoughts, the result is a depressive, anxious, angry or other symptoms that precipitate the behaviour of risk habit such as chewing to overcome it (Brown RA et al. 2003). The thoughts with a clear message of positivity or negativity should be recorded and it is curcial to discern which type of thoughts dominates in this process. The negative thoughts can be managed with the coping skills that they were thought before. The main researcher will brief all participants regarding this thought management through a talk.

Checkpoint 2 will be prepared for completion practice for Positive and Negative Thoughts worksheet (Appendix L). One of their current positive and negative thoughts will be used as a practice. At the end of session 5, **Checkpoint 3** will be prepared as saliva collection counter for participants to provide their 22-day saliva samples.

[figure not shown]

Figure 3.12 Summary of Participants' Flow on the 5th Session of the Intervention (Day 22)

3-month follow up (Day 90)

On **3- Month follow up**, participants will be assessed of their chewing abstinence through a follow up questionnaire after registration (**Checkpoint 1**). The items that will be required are brief personal particulars, participant's current chewing status, number of cut-down of habit by the participants (quid/day) and BQ composition if participants are still chewing. All participants will be motivated and encouraged regardless their success in quitting the BQ behaviour. A repeated educational talk of adverse effects of AN and BQ chewing habit will be given. A summary of community perception will be informed to the participants and they will be encouraged to contact research team if they needed any form of help in cessation in the future.

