3.11.5 LCMS analysis

The lab test will be run by staff at the Biotechnology Research Institute (BRI), Universiti Malaysia Sabah (UMS). The BRI lab is located at Kota Kinabalu, Sabah which is about 1 to 1.5 hours from the study site and precaution will be taken to deliver samples within 8 hours after collection due to the quick disappearance property of areca nut biomarkers after 8 hours of collection.

LCMS analysis will be carried out on a model Accela ultra HPLC system coupled to a Q Exactive Orbitrap Mass Spectrometer and a CTC PAL autosampler (all from Thermo-

Fisher, San Jose, CA). 10 µl of the above mixture will be injected into a Kinetex C18 column (150 x 3 mm, 2.6 µm, Phenomenex, Torrance CA) with a Phenomenex UHPLC C18 pre-column (3.0 mm i.d.).

Gradient elution will be performed at a flow rate of 300 µL /min using 10 mM ammonium hydroxide in H₂O (A) and 10 mM ammonium hydroxide in MeOH (B) as follows: 0-15.0 min linear gradient from 65%A to 20%A; 15.0-20.0 min hold at 20%A; 20.0-20.1 min increase to 65%A then to equilibrate it for 5 minutes. Total HPLC time including equilibration will be around 25 minutes.

Mass analysis will be performed under positive and negative electrospray full scan mode, the conditions will be as follows: (+) ESI spray voltage 4.5 kv, capillary transfer temperature 350 °C, (-) ESI spray voltage 3.5 kv, capillary temperature 320 °C; and other parameters will be: HESI heater temperature 200 °C, sheath gas flow rate 30 unit; auxiliary gas 5 unit, in-source CID 5 ev, scan range 100 ~ 1000. AGC target 1e6, maximum injection time 100 ms, resolution 35,000, microscan 1.

Quantitation of all analytes will be performed with Xcalibur™ software by extracting the within 5 ppm of the calculated exact masses as according: Arecoline and Arecoline-d5 at +ESI [M+H]⁺ 156.10191 and 161.13329; Guvacoline at +ESI [M+H]⁺ 142.08626, Guvacine at +ESI [M+H]⁺ 128.07061, Arecaidine at +ESI [M+H]⁺ 142.086, NNN at +ESI [M+H]⁺ 178.09749, NAT at +ESI [M+H]⁺ 190.09749, NNK and NNK-d3 at +ESI [M+H]⁺ 208.10805 and 211.12688, Nicotine and Nicotine-d4 at +ESI [M+H]⁺ 163.12297 and 167.14808, Cotinine and Cotinine-d3 at +ESI [M+H]⁺ 177.10224 and 180.12107, N-nitrosoguvacoline at +ESI [M+H]⁺ 171.07642, Hydroxycotinine at +ESI [M+H]⁺ 193.09715, and chavibetol at -ESI [M-H]⁻ 163.07590 (Franke AA et al,2015).

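### Day 22 saliva follows a 1–2 h session in the intervention arm only, with time since last chew neither equalised nor recorded, which is likely to favour that arm on the biomarker

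*Protocol*

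**What the plan says.** **Intervention arm, Day 22** (Protocol 3.10.3.2, 5th Session). Participants register, complete the follow-up questionnaire, join a discussion, hear a talk and practise a worksheet. Saliva comes last: "At the end of session 5, Checkpoint 3 will be prepared as saliva collection counter for participants to provide their 22-day saliva samples". Under the 1st Session heading, participants are told that "each support session will consume approximately 1-2 hours".

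**Control arm, Day 22** (3.10.3.2, Control Group). "Follow-up questionnaire and saliva samples will be taken on 22-day and 3-month". No order, waiting time or clock time is given. Section 3.1 states that "The control group will only receive an educational booklet", so there is no session on that day.

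**Baseline.** Both arms give saliva at Checkpoint 3, after the interview and the booklet. The later sampling point at Day 22 is therefore new, and it is described for one arm only.

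**Marker kinetics** (2.11). The four areca alkaloids "peaked within the first 2 hours post-chewing before returning to baseline levels after 8 hours". The same section concludes that salivary markers can be followed only up to 8 h after chewing.

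**Use of the markers.** Section 3.12.2 makes them the secondary outcome at Day 22 and Month 3. They are read against fixed cut-offs (arecoline 60, arecaidine 10, guvacoline 20, guvacine 6 and cotinine 10 ng/mL), and a value above the cut-off means still chewing. Sections 3.14.2 and 3.14.3 also use them to verify self-report. The primary outcome (3.12.1) is self-reported quitting.

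**Timing controls.** The collection procedure (3.11.1) sets no interval since the last chew. The follow-up form (Appendix M) has no field for time of last chew or time of collection.

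**The concern.** A marker that lasts only hours and is read against a fixed cut-off depends on when the sample is taken. Two equally chewing participants, one per arm, who arrive the same time after their last quid would be sampled at different points on the curve. The intervention participant would be sampled later by up to the length of the session. On the falling part of the curve, later sampling turns positives into negatives, and a negative is counted as cessation.

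Two results are at stake: the between-arm biomarker comparison at Day 22, and the biochemical check on self-reported quitting. Both would tend to look better in the intervention arm for a procedural reason. The error is systematic, so more participants would not reduce it.

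**Working it through.** The protocol gives no figure for this effect, so there is nothing to reproduce. The check is how large the effect could be under stated assumptions.

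**Inputs from the protocol**
- Session length L: about 1–2 h (3.10.3.2).
- Usable marker window: up to 8 h after chewing (2.11).
- Lightest eligible chewing: 2–3 episodes a week (3.8), that is 168/3 = 56 h to 168/2 = 84 h between chews.

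**Assumptions not in the protocol**
- A sample is positive up to W = 8 h after a chew. This equates the return to baseline with falling below the cut-offs.
- On arrival, time since last chew is uniform over the chewing interval T.
- Nobody chews during the session.
- Controls are sampled on arrival, so the arms differ by the whole of L.

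**Step 1: share of the window used.** 1/8 = 12.5% and 2/8 = 25%.

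**Step 2: false negatives among continuing chewers.** A sample taken L hours after arrival is negative if the last chew was more than W − L hours before arrival:

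FN(L) = max(0, (T − (W − L))/T), and excess = FN(L) − FN(0).

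| T | FN(0), on arrival | FN(1) | FN(2) | Excess, points |
|---|---|---|---|---|
| 4 h | 0% | 0% | 0% | 0 |
| 8 h | 0% | 12.5% | 25.0% | 12.5–25 |
| 12 h | 33.3% | 41.7% | 50.0% | 8.3–16.7 |
| 24 h | 66.7% | 70.8% | 75.0% | 4.2–8.3 |
| 56 h | 85.7% | 87.5% | 89.3% | 1.8–3.6 |
| 84 h | 90.5% | 91.7% | 92.9% | 1.2–2.4 |

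Once T is at least 8 h, the excess is simply L/T.

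**Step 3: sensitivity to W.** The zero at T = 4 h depends on W = 8 h. If levels stayed above the cut-offs for only 2–4 h, the excess at T = 4 h would be 25–50 points.

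**Step 4: effect on the arm comparison, T = 8 h.** Take the protocol's control rate of 9.09% (3.4) as the true quit rate in both arms, with 38 per arm. No continuing chewer is negative on arrival at this T, so the control arm reads 9.09%. The intervention arm reads 0.0909 + 0.9091 × 0.125 = 20.5%, or 0.0909 + 0.9091 × 0.25 = 31.8%. A two-sided 5% test that ignores clustering would then reject about 28% or 70% of the time, with no true difference.

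**Step 5: the same at T = 12 h.** The control arm reads 0.0909 + 0.9091 × 0.333 = 39.4%. The intervention arm reads 0.0909 + 0.9091 × 0.417 = 47.0%, or 0.0909 + 0.9091 × 0.5 = 54.5%. The spurious gap is 7.6–15.2 points.

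**The case against.** The strongest reply is that the size, and part of the direction, rest on things the protocol does not say.

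- **The control comparator is inferred.** The control order and waiting time at Day 22 are not stated, and the flow figure is not available. Both arms complete a follow-up interview. If that interview counts towards the 1–2 h in the intervention arm and precedes saliva in the control arm, the true difference is shorter than the session. This stands: 1–2 h is an upper figure for the gap.
- **A chew-free session is an inference.** It is plausible, but no text bars chewing. This stands as an assumption.
- **A reader might infer that later sampling always lowers the reading.** The documents do not support that. With a peak within 2 h, someone who chewed just before arrival may be sampled nearer the peak after a session. For an above/below reading this does not reverse the bias, provided levels pass the cut-off soon after chewing. That proviso is itself assumed, so the direction is likely rather than certain.
- **The window is not tied to the cut-offs.** Nothing links the return to baseline with the specific ng/mL values, and the kinetics in 2.11 are given for the areca alkaloids, not for cotinine. This stands and is why no single size can be given.
- **A reader might extend the point to Month 3.** The intervention text mentions a repeated talk and a saliva counter at the second of two checkpoints. It gives neither the talk's length nor its position relative to saliva. The problem is possible there but not shown.
- **A reader might treat the 8 h in Section 3.11.5 as part of the arm bias.** That wording concerns delivery to the laboratory and applies equally to both arms.

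None of this removes the documented fact: at Day 22 the sampling point follows a session in one arm only, and the data that would show the consequence are not collected.

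**Conclusion.** The point holds for Day 22. As written, the plan gives an arm-dependent sampling point for a short-lived marker and neither equalises nor records time since last chew. The likely effect is to favour the intervention on the secondary biomarker outcome and on the verification of self-report.

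The size cannot be fixed from the documents. With an 8 h positive window, no chewing in the session, controls sampled on arrival and the full 1–2 h delay, the excess of false negatives among continuing chewers is:
- 0 points if they chew every 4 h or more often;
- 12.5–25 points at 8 h intervals;
- about 8–17 points at 12 h;
- about 4–8 points at 24 h;
- about 1–4 points at 56–84 h.

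A reader might infer that the trial's main result is compromised. It is not: the primary outcome is self-reported by questionnaire, and at Day 22 the intervention arm completes that questionnaire before the discussion starts. The sample size is not affected either.

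**What to change.** 1. In both arms, collect saliva at the same point at Day 22: on arrival, before any discussion, talk or worksheet. Do the same at Month 3 for consistency, and state the order of steps for the control arm.
2. Add two fields to the follow-up form (Appendix M): clock time of collection and self-reported time of last chew. Arrival sampling does not by itself equalise time since last chew, but these fields let any remaining difference between arms be seen.
3. As a separate wording point, reconcile Section 3.11.5, which justifies prompt delivery "due to the quick disappearance property of areca nut biomarkers after 8 hours of collection", with Section 2.11, where the 8 h is counted from chewing.

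**Cost.** Stations are reordered and two items are added. No extra visits or samples are needed.

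**Downside.** Intervention-arm samples wait 1–2 h longer in the cooler. Adding the 1–1.5 h journey in Section 3.11.5 gives 2–3.5 h from collection to laboratory. That is within the 8 h of Section 3.11.5 but can exceed the 2–3 h transport statement in Section 3.14.1. The main researcher collects and transports the samples and also gives the Day 22 talk, so the handling arrangement should be settled when the order is changed.

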3.4 Sample Size

The sample size needed for this study will be calculated from a previous study performed by Herzog TA et al. (2022). The sample size was calculated using OpenEpi Version 3 software with the following assumptions:

 Margin of error (α error)	:	0.05
 Power of study ($1-\beta$)	:	0.8
 Allocation Ratio	:	1
 Percent of Exposed with Outcome	:	38.64 %
 Percent of Unexposed with Outcome	:	9.09 %

A total of 76 participants are needed for this study and 38 participants in each arm. After calculation of 20% dropout at 22th day and in 3 months (16 people), a revised total of 92 participants are needed for this study with 46 participants in each arm (Figure 3.1)

[figure not shown]

[figure not shown]
Figure 3.1 Flow of the Participant Allocation in the Study

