The community screening program for the intervention group will be organised at the community hall on a Saturday. Villagers who attend the screening program will first be registered and screened for eligibility to participate in the study (**Checkpoint 1**). The eligible participants will be briefed on the nature of the intervention and will be invited to participate. A copy of 'Patient Information Sheet' (PIS) (Appendix A) will be given for the reference about the study details and written informed consents (Appendix B) will be obtained from the villagers prior admitting them into the study.

Only consented participants will be interviewed by the trained interviewers (**Checkpoint 2**). Face-to-face interviews will be carried out to gain participant's information regarding demographics details and baseline information of BQ chewing behaviours, BQ composition, BQ dependency levels, reasons for chewing, readiness and self-perceived barriers to quit habit. No intra-oral clinical examination will be carried out in this study.

Upon completion of the interview, participants will be briefly explained and given an educational booklet which contains general information regarding AN and BQ, risk associated with BQ chewing behaviour, cessation strategies that are modeled after tobacco cessation and researcher's contact information. They will then be ushered to saliva collection counter (**Checkpoint 3**) to provide their baseline saliva sample.

Participants will be thanked and given a token of appreciation before being ushered out of the community hall and will be reminded to return the next day (Sunday) to initiate the first support session for the cessation intervention. For every intervention session attended by the participants, they will be monetarily incentivized for their time and commitment for cessation. Appointment card will be provided to ease participants reference of support session dates.

A self explanatory video presentation regarding general information of AN and BQ, the ill health effects of BQ and introduction and importance of cessation program will be continuously played **for the non- chewers in the village hall** to increase their knowledge and awareness while they are waiting for their family members. who are undergoing the screening. This can help maximise their support for their loved ones who are trying to quit the risk habit.

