Checkpoint 2 will be prepared as a saliva collection counter for participants to provide their 3-month saliva samples. Participation on each session of the intervention and follow-up will be monetarily incentivized to maximise the participation rate.

[figure not shown]

Table 3.13 Summary of Participants' Flow on the 3-Month Follow up of the Intervention (Day 90)

Table 3.4 Descriptive Summary of Intervention Arm Activities

Session	Day	Description of Session	By: Brown (2003), Moss et al (2015)	Document Reference
1	1	
Introduction of program, ground rules, informed consent
 
 • Health effects of AN and BQ chewing, esp. oral cancer risk • Discussion on self - monitoring for triggers (logs introduced) • Discussion on trigger management log (logs introduced) • Discussion on concept of arecoline fading and rate reduction prior to quitting (log introduced) 		
Appendix D
 
Appendix E
 
Appendix F

2	8	
Review trigger logs, discuss self - management approach
 
 • Discussion on lifestyle change to support quitting (logs introduced) • Discussion on "excuses" for not chewing, usage of "fake chew" • Explanation about brief relaxation exercise and coping skills • Reminder to participants about arecoline fading and that Quit Day is morning of the next session 		
Appendix I & J
 
Appendix G & H

3	15	
QUIT DAY. Facilitator is tasked with reminding participants to be supportive and non-judgmental, regardless of individual chewing status
 
 • Remind participants that withdrawal symptoms, if applicable, are generally worse in first 2 weeks, but will pass • Discuss coping strategies to prevent relapse • Plan to maximize social support for non – chewing (eg. talk) (log introduced) • Recommend physical activity (if applicable) 		
Appendix K

4	18	
Overall discussion of quitting experiences, including coping with triggers and high - risk situations, short - term benefits from quitting chewing
 
 • Discussion on negative health effects of AN/BQ chewing again, including oral cancer risk (reinforcing this throughout derived from pilot testing) • Discuss additional strategies for coping with urges to chew 		

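### The protocol text describes payment for attending the outcome visits only for the intervention arm, which may make follow-up differ by arm

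*Protocol*

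**What the plan says.** Protocol 3.10.3.2 takes the two arms in turn.

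- **Both arms, screening.** Each arm receives a token. For controls: "Participants will be thanked and given a token of appreciation before they are ushered out of the community hall".
- **Control, afterwards.** Participants receive an appointment card for Day 22, Month 1 and Month 3. The follow-up questionnaire is completed at all three visits, with saliva at Day 22 and Month 3. No payment is mentioned.
- **Intervention, sessions.** For each session attended, "they will be monetarily incentivized for their time and commitment for cessation". Session 5 falls on Day 22 and includes the follow-up questionnaire and the Day 22 saliva sample.
- **Intervention, Day 90.** The text closes with: "Participation on each session of the intervention and follow-up will be monetarily incentivized to maximise the participation rate".

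Section 3.12.1 defines both primary outcomes as self-reported quitting, taken from the follow-up questionnaire at Day 22 and at Month 3. Section 3.4 makes a single allowance for loss: "After calculation of 20% dropout at 22th day and in 3 months (16 people), a revised total of 92 participants are needed". Section 3.15.2 bases the cessation rates on participants who attended all sessions.

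**The concern.** Paying people to come to intervention sessions can be part of the programme, and controls have no such sessions. Paying people to come to the outcome assessment is different, because both arms have that visit and it should be conducted in the same way in each. The protocol itself expects money to affect attendance. That is the stated purpose of the Day 90 payment, and section 2.7 reports that incentives raised participation in the earlier cessation programme.

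If one arm is paid at Day 22 and Month 3 and the other is not, the proportion and the kind of people who return may differ by arm. The restriction in 3.15.2 makes this more consequential, since attendance decides who is counted. An analysis plan can examine unequal follow-up afterwards, but it cannot make the visits equal.

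**Working it through.** **Step 1. The arms side by side (3.10.3.2).**

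| Visit | Control text | Intervention text |
|---|---|---|
| Screening | token | token |
| Day 22 (primary outcome) | appointment card, no payment mentioned | paid, as Session 5 |
| Month 1 | appointment card, no payment mentioned | no visit described in this section; 3.14.3 lists one |
| Month 3 (primary outcome) | appointment card, no payment mentioned | paid, as follow-up |

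The intervention text lists token and money separately, so the control token cannot be read as the same incentive. The arms match at screening and differ, as written, at both primary time points.

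**Step 2. What the sample size assumes (3.4).** Inputs: α 0.05, power 0.80, p₁ = 0.3864, p₂ = 0.0909, 1:1 allocation. The protocol states: "A total of 76 participants are needed for this study and 38 participants in each arm".

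Without continuity correction, two-sided: n₀ = [1.960 × √(2 × 0.23865 × 0.76135) + 0.842 × √(0.3864 × 0.6136 + 0.0909 × 0.9091)]² / 0.2955² ≈ 31.5, so 32 per arm. With the correction: n = (n₀/4) × [1 + √(1 + 4/(n₀ × 0.2955))]² ≈ 37.9, so 38 per arm. The plan's 76 is reproduced.

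The 92 follows as 38 × 1.2 = 45.6, rounded up to 46 per arm. The allowance is therefore 46 − 38 = 8 people in each arm, the same in both.

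**Step 3. Is power the problem?** With 46 per arm, loss unrelated to outcome, the plan's quit rates, a normal approximation without continuity correction, and individuals treated as independent as in 3.4:

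| Assumed loss (intervention / control) | Power |
|---|---|
| 20% / 20% | 0.86 |
| 10% / 30% | 0.85 |
| 10% / 40% | 0.81 |

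Power falls little, so the risk is bias, and a larger sample would not remove it.

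**Step 4. Illustration with missing counted as still chewing.** The loss splits are assumptions; the protocol gives only 20% overall. With the same true quit rate p in both arms, the false difference is p × (1 − loss in intervention) − p × (1 − loss in control) = p × (difference in loss).

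| True rate p | 10% / 30% loss | 10% / 40% loss |
|---|---|---|
| 9.09% | 0.0909 × 0.20 = 1.8 points | 0.0909 × 0.30 = 2.7 points |
| 20% (assumed) | 0.20 × 0.20 = 4.0 points | 0.20 × 0.30 = 6.0 points |
| 38.64% | 0.3864 × 0.20 = 7.7 points | 0.3864 × 0.30 = 11.6 points |

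All favour the intervention, because control is assumed to lose more.

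**Step 5. Illustration with missing people dropped.** The observed rate is p(1 − L_q) / [p(1 − L_q) + (1 − p)(1 − L_c)], where L_q is the loss among quitters and L_c among chewers. Take a true control rate of 9.09%:

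- Quitters lost more (40% against 25% of chewers): 0.0909 × 0.60 / (0.0909 × 0.60 + 0.9091 × 0.75) = 7.4%.
- Chewers lost more (35% against 20% of quitters): 0.0909 × 0.80 / (0.0909 × 0.80 + 0.9091 × 0.65) = 11.0%.

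The control rate can move either way. If loss is unrelated to quitting (L_q = L_c), it does not move at all.

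**The case against.** The strongest reply is that the protocol nowhere says controls go unpaid. The Day 90 sentence names no arm, it closes the account of implementation, and its purpose applies equally to controls. The control text gives the return visits little space, so its silence is weak evidence. The information sheet and consent form (Appendices A and B) and the control flow in Figure 3.6 could not be read here, and a control payment may be described there. This stands against asserting that controls are unpaid. It does not remove the asymmetry: the sentence sits under the Intervention group heading, and the control procedures contain no counterpart.

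Three stronger readings are tempting and are not supported.

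- **That loss will differ, and will bias the result however missing people are handled.** Neither is certain. Five sessions of one to two hours could raise dropout in the intervention arm instead, and Step 5 shows no complete-case bias when loss is unrelated to quitting.
- **That money rewards reporting that one has quit.** The words about commitment attach to attendance at sessions, not to follow-up and not to chewing status. Participants are to be encouraged whatever their success, and saliva is taken in both arms at Day 22 and Month 3 to verify self-report.
- **That any single figure in Step 4 estimates the bias.** The loss splits are assumed, and the protocol does not state a rule that missing counts as chewing.

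**Conclusion.** The point holds as a gap in the conduct section. The protocol text describes payment for attending the outcome visits only for the intervention arm, and does so at both primary time points. Followed as written, this may produce different attendance by arm and could bias the cessation comparison. It is a risk inferred from the design, not an effect the documents demonstrate.

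Its size cannot be derived from the documents, nor can its direction if missing people are dropped. Under the assumptions of Step 4 with 10% against 30% loss, the false difference runs from about 1.8 to 7.7 points across the plan's two quit rates, compared with a planned difference of 38.64 − 9.09 = 29.55 points. The illustration is therefore well below the planned effect, but not negligible if the true effect is smaller. The correction is cheap and should be made.

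**What to change.** In 3.10.3.2, state in both the Control Group and the Intervention group text that every participant receives the same payment for attending the Day 22, Month 1 and Month 3 assessments, as compensation for time and regardless of chewing status. Keep payment for intervention sessions as a separate item. At Day 22, where Session 5 and the assessment coincide, separate the assessment payment from the session payment. As an optional clarification, describe the session payment as compensation for time only, without the reference to commitment.

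The cost is a small payment to each control participant at up to three visits. With the planned 46 controls that is at most 46 × 3 = 138 payments; it could be more, because section 3.6 recruits all eligible people in each village. If equal payment was already intended, the change is wording only.
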